8.3 Missing Data

For participants who are withdrawn from the study prior to the end of the study, all data collected up to the point of discontinuation will be used for analysis.

Imputation will be performed on post-baseline viral loads depending on the viral load results as below:

This document is confidential.

Viral loads that are missing or less than the LLOD (453) will be imputed as $0.5 \times \text{LLOD} = 0.5 \times 453 = 226.5$ copies/ml = 2.36 log10c/ml.

Viral loads that are above the LLOD but lower than the LLOQ (1570) will be imputed as $\text{LLOQ} - 0.5 \times (\text{LLOQ} - \text{LLOD}) = 1570 - 0.5 \times (1570 - 453) = 1011.5$ copies/ml = 3.00 log10c/ml.

Possible VL results	LLOD	LLOQ	Reported in the listings as:	Imputation for analysis:
Missing (as Ct>45)	453	1570	NEG	Half LLOD = 226.5 copies/ml = 2.36 log10c/ml
<LLOD, e.g. 400	453	1570	NEG	Half LLOD = 226.5 copies/ml = 2.36 log10c/ml
Between LLOD and LLOQ, e.g. 1000	453	1570	<1570	LLOQ - 0.5*(LLOQ-LLOD) = 1011.5 copies/ml = 3.00 log10c/ml
>LLOQ, e.g 2000	453	1570	Numeric result	None – use numeric result

For calculating age, birth date will be imputed as follows:

For all subjects, the missing date and month will have this imputed as '30th June'.

Birth date will be presented in listings as 'YYYY'.

Completely missing dates of birth will remain as missing, with no imputation applied. Consequently, the age of the subject will not be calculated and will remain missing.

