8.2.1. Inclusion Criteria

1. Adult patients aged ≥ 18 years
2. IC (as defined in the clinical commissioning policy [NHS England, 2022])
3. A positive PCR or antigen test for SARS-CoV-2 through clinical testing or routine screening undertaken as part of clinical management
4. Prescribed treatment with sotrovimab as standard of clinical care
5. Able to provide informed consent and willing to adhere to study-related procedures

The list of IC population eligible to receive sotrovimab will be derived from the IC cohorts outlined in the interim Clinical Commissioning Policy: neutralising monoclonal antibodies or antivirals for non-hospitalised patients with COVID-19. Patient cohorts considered at highest risk from COVID-19 and to be prioritised for treatment with nMABs [NHS England, 2022]. The list may include specific IC patients within the following cohorts:

- Patients with a solid cancer
- Patients with a haematological disease and stem cell transplant recipients
- Patients with renal disease
- Patients with liver disease
- Patients with immune-mediated inflammatory disorders (IMID)
- Immune deficiencies
- HIV/AIDS
- Solid organ transplant recipients

Of note, the criteria for the IC cohorts are subject to change as they will follow the latest NHS guidance. The protocol will not be amended to accommodate updates to MHRA guidance, but the criteria will be updated accordingly in the study reference manual.

The decision to treat patients with sotrovimab will be made prior to and independently from the decision of enrolling patients into this study by the patient's healthcare team. Informed consent form and baseline sample collection will be taken prior to sotrovimab administration or if not possible, then either during sotrovimab infusion or as close as possible to the end of sotrovimab infusion (within ≤ 2 hours of the end of the sotrovimab infusion). This study will therefore include patients who have received sotrovimab dosed as part of their standard clinical care

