7.3 Virology Set

The Virology Set (VS) will include all participants who were enrolled and exposed to study intervention with a positive PCR test by GOSH qPCR having Viral load above lower limit of detection (i.e., viral load \geq LLOD) as threshold at baseline.

This document is confidential.

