- AA changes in the SARS-CoV-2 spike consensus sequences from baseline in samples where viral load is insufficient for >5% allelic frequency analysis but sufficient to generate consensus level sequencing data

For the above endpoints, Baseline and post-baseline (Day 7, 14 and 28 (+/-2 days)) AA substitutions will be summarized by showing the counts and percentages of patients in spike and epitope substitutions separately for Minority species (>5% allelic frequency) as well as consensus sequence (>50% allelic frequency).

Treatment emergent AA substitutions in spike as well as epitope for minority species and consensus sequence would be listed separately.

A similar baseline and post-baseline AA substitutions summary were presented by VOC/VUI variants for the interim but will not be included in the final analysis..

Data listings will be provided for all the baseline and post-baseline AA substitutions in spike as well as epitope for minority species and consensus sequence separately.

- Viral load

Absolute and change from baseline viral load summaries will be based on Safety and Virology population respectively on log10 copies/mL.

An overall summary of viral load (log10 copies/mL) with actual values and change from baseline values of viral load as well as by Day 0, Day 7, 14 and 28 (+/-2 days) using descriptive statistics will be displayed and presented graphically over time.

In addition, viral load (log10 copies/mL) with actual values and change from baseline values will also be summarized by VOC/VUI variants, and for Epitope Substitutions by Residue and presented graphically over time. Also, individual subject profile plots of viral load by VOC/VUI will be graphically presented based on viral load imputed values.

.A summary of viral load (log10 copies/mL) with actual values using descriptive statistics will be presented for the subset of subjects who had missing viral load at Baseline, and separately for the subset of subjects who had a viral load available at Baseline.

Listings will be provided for all viral load data as well as a separate listing including only epitope substitution.

This document is confidential.

- **Viral Rebound**

A subject has experienced a virologic rebound when following conditions are met:

If subject is in the safety population and:

- Viral load increases $>1 \log_{10}$ copies/mL at any point in time following any previous sample.
OR

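### SAP 8.3 substitutes values for low viral loads after baseline only, so Day 0 and later visits are handled differently; minor, and cured by one rule for all visits

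*SAP*

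**What the plan says.** The substitution rule is in SAP 8.3. Its scope is set by the sentence "Imputation will be performed on post-baseline viral loads depending on the viral load results as below". Results with no amplification or below the LLOD (453 copies/mL) become 226.5. Results between the LLOD and the LLOQ (1570 copies/mL) become 1011.5. Results above the LLOQ are used as measured. The definitions of baseline value and change from baseline in SAP 8.2 add no rule for a low Day 0 load.

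SAP 10.2 then uses Day 0 in four ways:

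- It assigns the sets: "Absolute and change from baseline viral load summaries will be based on Safety and Virology population respectively on log10 copies/mL".
- It tabulates Day 0 with the later visits: "as well as by Day 0, Day 7, 14 and 28 (+/-2 days) using descriptive statistics will be displayed".
- It says that "individual subject profile plots of viral load by VOC/VUI will be graphically presented based on viral load imputed values" (Figure 1.4), although no imputed Day 0 value exists.
- It defines rebound, in the Safety Set, as a rise of more than 1 log10 after any previous sample, or as a load becoming quantifiable after being below the LLOQ or LLOD. It does not say whether tested or imputed values are compared.

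Low central results at Day 0 can occur. Protocol 8.2.1 admits patients on "A positive PCR or antigen test for SARS-CoV-2 through clinical testing or routine screening undertaken as part of clinical management", and SAP 7.3 separately restricts the Virology Set to those with a "positive PCR test by GOSH qPCR having Viral load above lower limit of detection" at baseline.

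The lowest band is also worded in two ways within SAP 8.3. The prose reads "Viral loads that are missing or less than the LLOD (453) will be imputed as" half the LLOD. The table row beside it is narrower: "Missing (as Ct>45").

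**The concern.** The same laboratory result is treated one way at Day 0 and another way afterwards. A Day 0 swab with Ct>45 has no value and leaves the mean; the same result at Day 7 enters as 2.36 log10. A numeric Day 0 result below the LLOQ stays as recorded; the same number later is replaced. Part of any difference between Day 0 and later visits would then come from the data rule and not from the virus.

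At stake are the Safety Set viral load summaries by visit, to a small degree the change-from-baseline tables, and the rebound count when Day 0 is the reference sample.

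**Working it through.** **Inputs.** LLOD 453 and LLOQ 1570 copies/mL (SAP 8.2); substitution rule (SAP 8.3); analysis sets and rebound criteria (SAP 7.3, 10.2). The documents do not say how many patients fall in each band, so shares and means below are marked as assumptions.

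**1. The plan's own figures.** 0.5 × 453 = 226.5, log10 = 2.355 (SAP: 2.36). 1570 − 0.5 × (1570 − 453) = 1011.5, log10 = 3.005 (SAP: 3.00). Both reproduce. The difficulty is where the rule applies, not its arithmetic.

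**2. Safety Set means by visit (Table 1.161).** Let q be the share of tested Day 0 swabs that are negative and left without a value, and M the mean log10 load of the rest. As written, the Day 0 mean is M. With the same rule as later visits it is (1 − q)M + 2.355q. The difference, q(M − 2.355), is added to the apparent fall. With q and M assumed:

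| q | M = 5 | M = 6 | M = 7 |
|---|---|---|---|
| 5% | 0.13 | 0.18 | 0.23 |
| 10% | 0.26 | 0.36 | 0.46 |
| 15% | 0.40 | 0.55 | 0.70 |

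**3. Numeric Day 0 results below the LLOD, kept as recorded.** An unchanged load of 400 (the SAP's own example value) shows log10(400) = 2.602 at Day 0 and 2.355 later: a false fall of 0.25. An unchanged load of 100 shows 2.000 and then 2.355: a false rise of 0.36. The direction is not fixed.

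**4. Change from baseline (Virology Set).** Baselines here are at or above 453, so footing is unequal only if the baseline is 453 to <1570 and the later value is below the LLOQ. The error is then log10(1011.5/baseline):

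- baseline 453: +0.349
- baseline just under 1570: −0.191

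For example, a baseline in this band followed by a negative shows log10(226.5/453) = −0.30 to log10(226.5/1570) = −0.84. With equal substitution it is log10(226.5/1011.5) = −0.65 throughout.

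Averaged over the band, the error is +0.024 if baselines are spread evenly in copies and +0.079 if evenly in log10 (assumptions). If 5–20% of baselines lie in the band (assumption) and all their later values are below the LLOQ, the cohort mean moves by 0.05 × 0.024 = 0.001 to 0.20 × 0.079 = 0.016 log10.

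**5. Rebound, first criterion.** A rise to a substituted 1011.5 exceeds 1 log10 if the raw Day 0 value is below 1011.5/10 = 101.15 copies/mL. For example, 100 then 1011.5 is +1.005. With the same substitution on both values it is log10(1011.5/226.5) = 0.65, which is not a rebound. The second criterion does not apply, because the later value is not quantifiable.

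Extending the SAP's two calibration points log-linearly (assumption), the slope is log10(1570/453)/(38 − 36.18) = 0.297 per cycle. About 101 copies then lies at Ct 38 + log10(453/101.15)/0.297 = 40.2, short of the Ct>45 cut-off, so such a value could be reported.

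**The case against.** The rows of the SAP 8.3 table are not labelled post-baseline, so the authors may have meant every visit. That is plausible, but the governing sentence says otherwise and a programmer would follow it.

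Tables 1.162 and 1.163 split the absolute loads by whether a baseline load exists. Table 1.163 keeps the same subjects from Day 0 onward and so removes the composition effect in step 2. This stands as a mitigation. It does not correct Table 1.161, and the SAP text does not say whether a tested Ct>45 swab counts as a missing baseline load. The shells, which are a separate document, may say so.

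When the later value is at or above the LLOQ, baseline and later value are both used as measured, so the plan is already consistent. For 453 rising to 5000, the plan gives log10(5000/453) = +1.04; substituting at baseline gives log10(5000/1011.5) = +0.69. A reader might infer that every change from a low baseline is wrong. The documents do not support that; step 4 is limited accordingly.

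A reader might also infer from the prose in SAP 8.3 that home swabs never returned will be counted as undetectable, inflating Secondary Objective 2 (Table 1.18). Read literally, the excess would be m(1 − p), for a share m of absent swabs and a true undetectable share p: 0.20 × (1 − 0.50) = 10 points down to 0.20 × (1 − 0.90) = 2 points, using as m the protocol's 20% loss to follow-up, which is per patient and not per visit. The documents point away from this reading. The table row is confined to Ct>45, its listing value is NEG, and SAP 8.1 and 12.2.5.2 base percentages on non-missing or observed data. What stands is a mismatch of wording.

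Finally, viral load change is not a listed primary or secondary endpoint.

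**Conclusion.** The concern holds, as a minor point. SAP 8.3 as written leaves Day 0 without a substitution rule while later visits have one.

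The main effect is on Table 1.161, where the fall after Day 0 would be overstated by q(M − 2.36). The 0.13–0.70 log10 range rests wholly on assumed q and M and on Day 0 swabs with Ct>45 being left without a value. Numeric Day 0 results below the LLOD can shift either way. In the Virology Set the error is +0.35 to −0.19 log10 for the subjects concerned and negligible for the cohort mean. A false rebound by the first criterion can arise from a raw Day 0 value below about 101 copies/mL followed by a substituted 1011.5.

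Figure 1.4 shows individual profiles, so its problem is raw or absent Day 0 points, not a biased mean. The documents do not show that absent swabs will be imputed. The primary sequence endpoints do not use viral load values in this way and are unaffected.

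**What to change.** In SAP 8.3, extend the substitution from post-baseline loads to viral loads at all visits including Day 0. In SAP 10.2, state that rebound compares tested swabs, with the same substitution on both values.

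Two wording reconciliations belong with this:

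- In the SAP 8.3 prose, replace the unqualified reference to missing loads with tested swabs that did not amplify (Ct>45), as in the table, and say that absent swabs stay missing.
- Define a missing baseline load for Tables 1.162 and 1.163 as no tested swab at Day 0, so that a tested negative is not grouped with an absent one.

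The cost is a few lines of text and minor reprogramming. The interim analysis has already been run (SAP 2.2) and included the viral load tables, so the final report needs a note, or a re-run of those tables, where the Day 0 rule changes them. The rebound table (1.44) is listed for the final analysis only.

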8.3.1 Missing Adverse Events (AE) and Medication Dates

Incomplete/missing AE/ Concomitant medication start and end dates are not expected, in case of incomplete/missing AE/Concomitant medication start and end dates, imputation will be performed as stated below.

Adverse Events	
Partial dates for AE recorded in the CRF will be imputed using the following conventions:
Missing start day
If study treatment start date is missing (i.e. participant did not start study treatment), then set start date = 1st of month.Else if study treatment start date is not missing:
If month and year of start date = month and year of study treatment start date then
If stop date contains a full date and stop date is earlier than study treatment start date then set start date= 1st of month.Else set start date = study treatment start date.	
----------------	---	--

This document is confidential.

		
 ○ Else set start date = 1st of month.
	Missing start day and month	
 • If study treatment start date is missing (i.e. participant did not start study treatment), then set start date = January 1. • Else if study treatment start date is not missing: 
 ○ If year of start date = year of study treatment start date then 
 ▪ If stop date contains a full date and stop date is earlier than study treatment start date then set start date = January 1. ▪ Else set start date = study treatment start date. ○ Else set start date = January 1.
	Missing stop day	Last day of the month will be used.
	Missing stop day and month	No Imputation
	Completely missing start/end date	No imputation

 • Completely missing start or end dates will remain missing, with no imputation applied. 		
Concomitant Medications/Medical History	Missing start day	
 • Partial dates for any concomitant medications recorded in the CRF will be imputed using the following convention: 
If study intervention start date is missing (i.e. participant did not start study intervention), then set start date = 1st of month.
 
Else if study intervention start date is not missing:
 
 • If month and year of start date = month and year of study intervention start date, then 
 ▪ If stop date contains a full date and stop date is earlier than study intervention start date, then set start date= 1st of month. ▪ Else set start date = study intervention start date.
		
Else set start date = 1st of month.

	Missing start day and month	
If study intervention start date is missing (i.e. participant did not start study intervention), then set start date = January 1.
 
Else if study intervention start date is not missing:
 
 • If year of start date = year of study intervention start date, then 
 ▪ If stop date contains a full date and stop date is earlier than study intervention start date, then set start date = January 1. ▪ Else set start date = study intervention start date.
	Missing end day	
Else set start date = January 1.
 
A '28/29/30/31' will be used for the day (dependent on the month and year).

	Missing end day and month	
A '31' will be used for the day and 'Dec' will be used for the month.

This document is confidential.

	Completely missing start/end date	No imputation
•		

8.4 Visit Windows

Analysis will be based on nominal visit, excluding all the unscheduled visits. Unscheduled assessments will be listed but will not be included in the summarization.

8.5 Pooling of Centers

Not Applicable since no adjustment for center or by center analyses are planned.

8.6 Subgroups

Not Applicable.

This document is confidential.

9. Demographic, Other Baseline Characteristics and Medication

9.1 Subject Disposition and Withdrawals

Subject disposition will be summarized for all subjects in the Screened Set. The summary table will show the number of subjects screened, the number of screen failures and reason for screen failures, and who discontinued the study prematurely along with the primary reasons for discontinuation.

Reasons for discontinuation of study will also be listed, including the time in days before discontinuation from study.

Eligibility criteria, and informed consent information will be listed for all subjects in the Safety Set.

Screening failures (including screen failure date and primary reason for failure) will be listed separately.

9.2 Protocol Deviations

Protocol deviations will be identified periodically throughout the trial following the 'Protocol Deviation and Non-compliance Management Plan' (Syneos Health SOP and WI, 3101 and 3101.W02). Final definition of protocol deviations and categorization into Not Important / Important will be performed in the Data Review Meeting (DRM) prior to database lock.

All protocol deviations related to study inclusion or exclusion criteria, conduct of the trial, patient management, dosing, and sampling procedures or patient assessment will be listed. The list of protocol deviations will be reviewed by the Sponsor, the principal investigator and the study statistician, and finalized before database lock during the DRM. All protocol deviations (Not important and Important) observed during the conduct of the study will be listed. Important protocol deviations (patients with at least one important PD overall and split by PD category) will be summarized for safety population.

9.3 Demographic and Baseline Characteristics

Demographic and baseline characteristics, including age, age group, sex, race, ethnicity, body mass index (BMI), current smoking status will be summarized for safety population using standard descriptive statistics. Further separate summary tables including demographic and baseline characteristics for subjects who did not clear the virus at D28 (viral load above LLOD at D28) and for subjects with sequence data available will also be presented.

In addition, duration of COVID-19 symptoms (days) prior to receiving sotrovimab, previous SARS-CoV-2 infection, Serostatus, if available the test used for serology, COVID-19 Disease History, Number of days since initial COVID-19 positive test result, Test used for COVID-19 testing, number of previous COVID-19 infections, COVID-19 Vaccination status, Product name of COVID-19 vaccine, number of doses of vaccine will also be summarized using standard descriptive statistics.

All demography data will be listed.

9.4 Medical History and Concomitant Diseases

Medical history, as recorded at screening/baseline and concomitant diseases, will be summarized separately for the safety population presenting the number and percentages of subjects within each CRF pre-defined classified conditions. Concomitant diseases are all events which are ongoing at first intake of study medication. A separate summary of medical conditions and comorbidities for subjects who did not clear the virus at D28 (viral load above LLOD at D28) and subjects with sequence data available will also be presented.

This document is confidential.

9.5 Prior and Concomitant Medication

Prior and concomitant medications will be coded by the Anatomical Therapeutic Chemical (ATC) classification system according to the World Health Organization Drug Dictionary (WHO-DD). Medications will be classified as concomitant or prior and summarized by ATC class (level 2, therapeutic subgroup) and preferred drug name for all subjects in the safety population.

Prior medication is defined as any medication taken before the date of the first dose of study treatment. Concomitant medication is defined as any medication taken on or after the date of the first dose of study treatment.

Concomitant medication will be recorded, including the medication name, daily dose, unit, regimen, administration route, reason for administration (text field) and medication start and end dates or ongoing. All prior and concomitant medications will be listed, with a flag identifying prior medications, for all subjects in the Safety population.

The summary tables will show the frequency and percentage of subjects in each group with at least one usage of medication on the sub-class level within each ATC class sorted alphabetically.

10. Efficacy

Treatment Emergent Amino acid Substitutions/Amino acid Change from Baseline is defined as any amino acid substitutions detected at post-baseline visits compared to baseline sequence.

